4.4 Randomization Procedures and Blinding

Eligible subjects will be randomized in a 1:1 ratio by means of Interactive Response Technology (IRT) to one of the following Treatment Sequences:

- IgPro20 0.5 g/kg/week for 16 weeks followed by IgPro10 2 g/kg/ 4 weeks for 16 weeks (Treatment Sequence A)
- IgPro10 2 g/kg/ 4 weeks for 16 weeks followed by IgPro20 0.5 g/kg/week for 16 weeks (Treatment Sequence B).

The randomization list will be generated by the IRT external service provider according to the approved randomization specifications. The IRT external service provider will keep the randomization code on file.

This is an open-label study, blinding procedures are not applicable.

4.5 Determination of the Sample Size

The sample size for this study is not determined as based on hypothesis testing considerations. The sample size is mainly based on feasibility, not driven by power calculations for statistical hypothesis testing. However, based on the 9 IgPro20 studies completed by CSLB (8 studies on PID and 1 study in CIDP), the rate of ISRs per IgPro20 infusion is expected to be approximately 0.1, with 0.5 likely to be the maximum. With the target sample size of 20 subjects (10 subjects per Treatment Sequence) and each subject receiving 28 IgPro20 SC infusions, there are a total of 560 planned IgPro20 infusions overall

for the entire study. If the rate of ISRs per infusion is 0.1, the study will have 80% chance to have a 95% CI with half width ≤ 0.0261 using Wilson score method; if the rate is 0.5, the half width of the 95% CI will be ≤ 0.0414 .

4.6 Interim Analyses Other Than Sample Size Re-estimation

An interim analysis is planned after 10 subjects have completed at least 8 weeks of IgPro20 treatment in either Treatment Period for the purposes of safety review and bioavailability.

The tables produced for the interim analysis will be a subset of the tables for the final analysis. No changes to the tables for the special purpose of the interim analysis will be done. Tables to be produced are marked in a separate document.

4.7 Interim Sample Size Re-estimation

Sample size re-estimation is not planned for this study.

5 Changes in the Conduct of Planned Analyses

The primary endpoint (CSP 2.1.2) requests to summarize AEs, TEAEs, AESIs, and SAEs in total and by severity and causality. In deviation to this, the summary of AEs will be restricted to TEAEs only.

In section CSP 2.2.2 “Secondary Endpoints” C_{trough} is defined as “minimum plasma drug concentration”. This is corrected to “trough plasma drug concentration”.

In section CSP 10.3.2.1 “Safety of IgPro20” 95% confidence intervals (CI) are requested for the rate of ISR per subject and per infusion. The CIs for the rate of ISR per infusion will not be calculated as the infusions are not statistically independent.

The Full Analysis Set (section CSP 10.2.1) is renamed to ITT Analysis Set, and the description was reworded for clarity. The definition of the set is not changed.

Section 10.4.2 of the CSP (Interim Analysis) states:

"An interim analysis is planned after all subjects randomized to Sequence A have finished IgPro20 treatment (Treatment Period 1). This interim analysis is planned for safety review and reporting."

The timing and purpose of the Interim Analysis has changed (see Section 4.6 of this SAP).

CSP section 10.3.3.1 requires "... subject as a random effect ..." in the model to assess relative bioavailability. This effect will not be applied.

6 Study Analysis Sets

6.1 Screened Analysis Set (SCR)

The SCR will comprise all subjects who provide informed consent/assent and who underwent study screening procedures.

6.2 Intent to Treat (ITT) Analysis Set

The ITT analysis set will include all subjects who are randomized, regardless of whether they received treatment.

6.3 Safety Analysis Set (SAF)

The SAF will comprise all subjects who receive at least 1 partial infusion of IgPro20 or IgPro10.

6.4 Safety Analysis Set IgPro10 (SAF-IgPro10)

The SAF-IgPro10 will comprise all subjects who receive at least 1 partial infusion of IgPro10.

6.5 Safety Analysis Set IgPro20 (SAF-IgPro20)

The SAF-IgPro20 will comprise all subjects who receive at least 1 partial infusion of IgPro20.

6.6 Per Protocol Analysis Set IgPro10 (PP-IgPro10)

The PP-IgPro10 will comprise all subjects for whom the dose-normalized baseline-corrected $AUC_{0-\tau}$ can be derived for the IgPro10 treatment period. Reasons for exclusion from the PP-IgPro10 (eg, potentially confounding concomitant medication or key protocol deviations) will be assessed case-by-base before database lock in the Data Review Meeting (DRM).

6.7 Per Protocol Analysis Set IgPro20 (PP-IgPro20)

The PP-IgPro20 will comprise all subjects for whom the dose-normalized baseline-corrected AUC_{0-tau} can be derived for the IgPro20 treatment period. Reasons for exclusion from the PP-IgPro20 (eg, potentially confounding concomitant medication or key protocol deviations) will be assessed case-by-base before database lock in the DRM.

7 General Considerations

Analysis datasets will be created according to CDISC standards, and data will be displayed according to reporting standards in this SAP.

SAS version 9.3 or higher will be used to perform all data analyses and to generate tables, figures, and listings.

Continuous variables will be summarized in terms of the number of observations, mean, standard deviation, median, Q1, Q3, minimum and maximum. Other descriptive statistics (eg, coefficient of variation) may be reported when appropriate. Categorical variables will be summarized using frequency counts and percentages. Additional statistical parameters will be defined together with analyses for which they are needed. Summaries of continuous variables that have some values recorded using approximate values (eg, < or >) will use the numeric part of the value in calculations. Listings will present the data in its original format.

All listings will include subject number, Treatment Sequence, Treatment Period, and basic demographics (age and sex).

Summary statistics of central tendency will be reported to one more decimal place than the collected data. Summary statistics of variability will be reported to one more decimal place than the commensurate measure of central tendency. For example, the mean and median for age will be reported to one decimal place because it is collected in full years. The standard deviation of age will then be reported to 2 decimal places.

Formatting for dates and times will be:

- Dates only – ddmmmyyyy (e.g., 03MAR2019)
- Times only – hh:mm or hh:mm:ss (as appropriate)
- Dates and times – ddmmmyyyy hh:mm or ddmmmyyyy hh:mm:ss (as appropriate)

Unless otherwise stated, all listings will be sorted by Treatment Sequence, Treatment Period, subject number, and then by visit date. If any of these variables do not apply to a listing, then that listing will use only those that do in the order given here.

Generally, only pre-specified planned times will be used in the summaries, statistical analyses, and calculations of any derived parameters; unscheduled readings will be included in the listings.

Actual, rather than planned, sampling times will be used in the derivation of PK parameters and in the individual concentration-time plots and listing of PK concentration data. Planned times will be used in the descriptive summaries and in mean plots. Concentration-time data will be listed according to actual sampling times relative to dosing time.

Assessment windows will not be defined for the purpose of classifying measurements obtained outside scheduled assessment times.

Deviations from the analyses in this SAP will be identified in the CSR.

7.1 Multicenter Studies

Data from all participating sites will be pooled prior to analysis. However, a summary of subject disposition by country will be produced.

7.2 Treatment Descriptors

Displays will be grouped by treatment (IgPro20, IgPro10), Treatment Sequence (Treatment Sequence A, Treatment Sequence B), Treatment Period (Treatment Period 1, Treatment Period 2) if applicable, and / or combinations. All outputs (tables, listings, and figures) will contain all elements to uniquely identify the level of aggregation.

A total column is added for selected displays as indicated in the display mock-ups.

7.3 Multiple Comparisons and Multiplicity

There is no statistical hypothesis testing for this study thus there is no adjustment for multiple comparisons or multiplicity.

7.4 COVID-19 Impact

During the course of this study, the global COVID-19 pandemic occurred, impacting the study in a variety of ways. This section describes how the impact of COVID-19 will be reported.

Subject Disposition: Study Treatment Discontinuation or Study Discontinuation

Subjects who experience either study treatment discontinuation or study discontinuation due to COVID-19 will have the reason captured in the eCRF. On the appropriate eCRF form to record either study medication discontinuation (“End of Treatment” form) or study discontinuation (“Conclusion of Subject Participation” form), a reason will be selected which includes a field for descriptive text. The reason can be either “Withdrawal by Subject,” “Physician Decision,” or “Other”. The associated free text field entry will be assessed at the DRM whether it is considered associated with COVID-19. When either treatment or the study is discontinued due to an AE or death, the specific corresponding AE is collected. Discontinuations due to COVID-19 adverse events will then be identified based on whether the MedDRA code for the AE is included in the broad COVID-19 standard MedDRA query (SMQ).

Cases of study treatment discontinuation or study discontinuation due to COVID-19 will be included in the summary of subject disposition.

Demographic and Baseline Characteristics

As only 3 subjects have been enrolled prior to the COVID-19 pandemic onset, demographic and baseline characteristics will not be summarized by COVID-19 period, ie before and after pandemic onset. COVID-19 pandemic onset will be considered to be 04-Mar-2020, the date of the first positive SARS-CoV-2 test in Poland (only Polish sites in the study by that date).

Subjects with enrollment date after the pandemic onset will be flagged in the listings of demographic and baseline characteristics.

Concomitant Medications

For concomitant medications which are linked to specific adverse events, the eCRF collects information to identify the specific adverse event. As described in the Adverse Events section, relevant adverse events will be identified by broad COVID-19 SMQ.

Concomitant medications used to treat COVID-19 associated adverse events will be flagged in the listing of prior and concomitant medications.

Adverse Events

Adverse events associated with COVID-19, which can include a clinically significant laboratory finding like a positive test result for COVID-19, will be reported by investigators. COVID-19 associated adverse events are identified via MedDRA coding. Relevant adverse events will be identified for reporting by the broad COVID-19 standard MedDRA query (SMQ). All COVID-19 associated adverse events will be included in standard AE tables.

An overview summary table of COVID-19 associated treatment-emergent adverse events (TEAEs), including number and percentages of subjects as well as the number of events, will be provided for the following:

- Any TEAE (related/not related)
- Any serious TEAE (related/not related)
- TEAE resulting in death (related/not related)
- TEAE leading to permanent discontinuation of IP (related/not related)
- TEAE leading to interruption of IP (related/not related)
- TEAE leading to withdrawal from study (related/not related)
- TEAE by severity (mild, moderate, severe, missing)

A listing showing all COVID-19 associated adverse events will be provided.

A descriptive table will be generated for all COVID-19 associated TEAEs by PT, including number of subjects, percentages of subjects, and the number of events.

COVID-19 Vaccinations

Sites will be prompted to inquire whether a subject has received a COVID-19 vaccination and to record each dose of the vaccine on the concomitant medications form along with the exact date of administration and manufacturer of the vaccine. Standardised Drug Grouping (SDG) from WHO Drug Dictionary will be utilized to identify COVID-19 vaccines using the narrow SDG 'Vaccines for COVID-19'.

For subjects receiving COVID-19 vaccination during the study all treatment-emergent adverse events occurring within 7 days of COVID-10 vaccination will be summarized by System Organ Class and preferred term.

Visit Modality, Missed Visits and Missing Assessments

Changes to subjects' visits caused by the COVID-19 pandemic will be captured for each subject in the eCRF, on the "Visit Status" form. The eCRF page includes different options for the primary visit modality, as well as whether the missed visit/alternate visit modality is due to COVID-19. Changes to visit modality may be a protocol deviation, or could be permitted via a contingency amendment; in either case, this data is captured. Since assessments (eg vital signs, laboratory data) collected at each visit are known, the data missing due to COVID-19 can be determined.

Assessments that were missed or required alternate visit modality (eg televisits or home health visits) due to COVID-19 will be summarized. In addition, number of subjects with missed visits or alternate visit modality, by visit, will be summarized. Data will be listed.

Missing assessment to be evaluated:

- Clinical laboratory tests
- ECG
- Pulmonary function tests
- Vital signs
- Body weight
- CCI components
 - CCI
 - CCI
 - CCI
 - CCI
 - CCI
- TEE Safety assessment
- Hemolysis assessment

Alternate visit modality:

- Visits without "Visit Status" form are considered performed as planned.
- Missing visits without "Visit Status" form are considered not missing due to COVID-19.
- Unscheduled visits cannot have alternate visit modality.

- In protocol, there are ‘Site Visits’, ‘Home Visits’, ‘Telephone Call’, and mixed ‘Site/ Home Visits’. Only site visits and some home visits are captured in eCRF using a visit form. Most home visits and the telephone call at EOS do not have a visit form, and consequently cannot have an alternate visit modality.

Protocol Deviations

Protocol deviations due to the COVID-19 pandemic will be collected in the Clinical Trial Management System (CTMS) per the study specific Protocol Deviation plan. Pandemic related protocol deviations are identified within CTMS using the term ‘Epidemic/Pandemic’ in column ‘Caused by Business Continuity Issue?’.

All COVID-19 related protocol deviations will appear in the listing of protocol deviations and will be flagged.

Missed Doses

Missed doses due to COVID-19 are identified using the Protocol Deviation tracker.

Overview of COVID-19 Impact

Number and percentages of subjects with at least one of the following due to COVID-19 will be summarized in an overview table:

- Subjects with Any COVID-19 Impact
- Protocol Deviations (key and non-key)
- Missed Doses
- Missing Assessment
- Missing Visit
- Alternate Visit Modality
- Study Treatment Discontinuation (by period)
- Study Discontinuation
- Any AEs/TEAEs
- Any Serious AEs/TEAEs
- Received COVID-19 Vaccine
- Concomitant Medications Received for Treatment of COVID-19

8 Data Handling Conventions

8.1 Missing Data

8.1.1 Imputation of Non-Date Missing Data

Missing data occurs when any requested data is not provided, leading to blank fields on the collection instrument. These data will be indicated by the use of a “blank” in subject listing displays. Answers such as “Not applicable” and “Not evaluable” are not considered to be missing data and should be displayed as such.

Subjects with the designation of treatment relationship for AEs and SAEs missing will have the worst case assumed to impute the relationship: if relationship to study treatment is missing it will be assumed to be “Yes”. There will be no other imputation for missing data other than as described in Section 8.1.2 for partial dates and times.

In the event that the study is terminated, all available data will be listed and a review carried out by the study team to assess which statistical analyses are to be performed.

8.1.2 Imputation of Partial Dates

Imputed dates will not be used to derive study day, duration, or elapsed time variables if not stated otherwise. Dates will be displayed in listings as recorded in the CRF.

Partial date imputation will follow ADaM conventions. The ADaM approach is to populate the numeric date variables with the imputed date and add a flag variable to the data set that indicates the level of imputation.

The flag variable can contain the values: blank, 'D', 'M', 'Y'.

blank: indicates that no imputation was done

D = 'Day': indicates that the day portion of the date is imputed

M = 'Month': indicates that the month and day portions of the date are imputed

Y = 'Year': indicates that the entire date (year, month, and day) is imputed

Adverse Events

Imputations in the adverse events dataset are used for slotting events to the appropriate study periods and for sorting in data listings. If an AE start or end date is missing, then the duration of the AE will be set to missing.

In general, an incomplete AE start date will be imputed such that the event starts as early as possible after the first IP infusion, irrespective of actual treatment.

Date	Missing Element	Rule
Start Date	day, month, and year	Do not impute completely missing AE start dates. The AE will be deemed treatment-emergent if the AE end date does not indicate that the AE ended prior to study treatment start date.
	day, month only	
 • If the study treatment start date is not missing: 
 • If the year of AE start date is the same as the year of study treatment start date • If the AE end date indicates the AE ended prior to study treatment start date then set AE month and day to January 1 • Otherwise set month and day of AE start date to study treatment start date • If the study treatment start date is missing then set month and day of AE start date to January 1.
	day only	
 • If the study treatment start date is not missing: 
 • If the month and year of AE start date is the same as the month and year of study treatment start date • If the AE end date indicates the AE ended prior to study treatment start date then set day of AE start date to the 1st of the month • Otherwise set day of AE start date to study treatment start date • If the study treatment start date is missing then set day of AE start date to 1st day of the month of AE start date.
End Date	any date element	No imputation for completely or partially missing AE end dates; the AE duration will be set to missing.

Medical History

End dates of Medical History are used to differentiate between past and current medical condition. If a partial end date is possibly after first IP intake the MH will be considered concomitant.

Date	Missing Element	Rule
Start Date	any date element	No imputation for completely or partially missing start dates
End Date	day, month, and year	Do not impute completely missing MH end dates. The MH will be deemed “concomitant”.
	day, month only	Set the end date to December 31.
	day only	Set the end date to the end of the month.

Concomitant Medication

Start and end dates will be imputed for use to derive the reference variables for concomitant medication start and end relative to treatment; any imputed dates will be included in analysis datasets with an identifier as imputed. The reference variables will be used to differentiate before, during and after treatment for the concomitant medication.

In general, an incomplete CM start date will be imputed such that the medication starts as early as possible after the first IP infusion, irrespective of actual treatment.

Date	Missing Element	Rule
Start Date	day, month, and year	Do not impute completely missing concomitant medication start dates; all values that depend on this date will be set to missing
	day, month only	
 If the study treatment start date is not missing: 
 If the year of CM start date is the same as the year of study treatment start date 
 If the CM end date indicates the CM ended prior to study treatment start date then set CM month and day to January 1 Otherwise set month and day of CM start date to study treatment start date If the study treatment start date is missing then set month and day of CM start date to January 1.
	day only	
 If the study treatment start date is not missing: 
 If the month and year of CM start date is the same as the month and year of study treatment start date 
 If the CM end date indicates the CM ended prior to study treatment start date then set day of CM start date to the 1st of the month Otherwise set day of CM start date to study treatment start date If the study treatment start date is missing then set day of CM start date to 1st day of the month of CM start date.

Date	Missing Element	Rule
	time	If the (imputed) start date of the medication is equal to the date of the study treatment start date, then set start time of medication to time of first study treatment start. Otherwise set to 00:00.
End Date	day, month, and year	Do not impute completely missing concomitant medication start dates; all values that depend on this date will be set to missing
	day, month only	If partial end date contains year only, set end date to the earliest of December 31 and the last visit in the study.
	day only	If the partial end date contains month and year, set the end date to the earliest of the last day of the end month reported and the last visit in the study.
	time	If the (imputed) end date is not missing then set to 23:59

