8.3.1 Study Periods for Adverse Events

AEs with onset date/ time at or after start of first infusion of study treatment are TEAEs. If the time of onset of an AE is missing: AEs with onset date at or after start of first infusion of study treatment are TEAEs. Assessment whether an AE is considered treatment-emergent, will take place after imputation of partially missing dates (see [Section 8.1.2](#)).

The TEAE analysis will be done for the study periods and groups shown in [Section 11](#). An AE will be counted for the analysis of a study period if the onset of the event falls within the study period. For the definition of start and end of the study periods see [Table 2](#).

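### A year-only AE start date in the year of first dosing always defaults to Period 1, so a Period 2 event is charged to the wrong product

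*SAP*

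**What the plan says.** SAP 8.1.2 (Adverse Events) gives the imputed date an allocation role: "Imputations in the adverse events dataset are used for slotting events to the appropriate study periods and for sorting in data listings". The general rule is that an incomplete start date is "imputed such that the event starts as early as possible after the first IP infusion, irrespective of actual treatment".

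The table below it then sets three cases.

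- **Month and day missing.** The condition is "If the year of AE start date is the same as the year of study treatment start date". If the end date shows that the AE was over before treatment, it goes to 1 January; if not, "Otherwise set month and day of AE start date to study treatment start date".
- **Day missing.** The condition is "If the month and year of AE start date is the same as the month and year of study treatment start date". If the end date shows that the AE was over before treatment, it goes to the first of the month; if not, "Otherwise set day of AE start date to study treatment start date".
- **Whole date missing.** "Do not impute completely missing AE start dates". The AE is treated as treatment-emergent unless its end date rules that out. No period is named.

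SAP 8.3.1 then allocates by onset: "An AE will be counted for the analysis of a study period if the onset of the event falls within the study period". SAP Table 2 ends Period 1 at the first infusion of the other product and runs Period 2 to end of study. SAP 11.2 builds the product columns from those periods: IgPro20 is A/1 plus B/2, and IgPro10 is A/2 plus B/1.

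**The concern.** Setting an uncertain start date to first dosing is a sound, cautious convention for deciding whether an AE is treatment-emergent. Here the same date also decides which product the AE belongs to, and for that purpose the convention is not cautious. It always points to whichever product came first.

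The direction depends on the sequence. In Sequence A, a misplaced IgPro10 event is added to IgPro20. In Sequence B, a misplaced IgPro20 event is removed from IgPro20 and added to IgPro10. The primary objective is the safety of IgPro20, so the Sequence B error understates the quantity of main interest. The extra ISR statistics in SAP 11.2 cover IgPro20 periods only, so a Sequence B ISR moved to Period 1 would drop out of them.

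SAP 8.2.1 already defines a reference date for Period 2, but the AE rule never uses it.

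**Working it through.** The plan gives no figure to reproduce. The check applies the SAP 8.1.2 rules to calendar dates.

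**Inputs.** Each period lasts 16 weeks = 112 days (Protocol glossary). With first infusion as day 1, crossover is day 113, or start + 112 days. Period 2 runs to end of study (SAP Table 2), nominally Week 36: 36 × 7 = 252 days, of which 252 − 112 = 140 are in Period 2.

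**Case 1: year only, same year as first dosing.** Start 01FEB2021; crossover 01FEB2021 + 112 days = 24MAY2021; true onset 20AUG2021, recorded as 2021. The years match and the AE did not end before treatment, so the imputed date is 01FEB2021. The AE goes to Period 1 and the wrong product. The same holds for every Period 2 AE recorded this way.

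How much of Period 2 is exposed depends on the start date:

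| First infusion (2021) | Period 1 days in 2021 | Period 2 days in 2021 | Period 2 share |
|---|---|---|---|
| 1 Jan to 1 Apr | 112 | 140 | 140/252 = 56% |
| 1 Jun | 112 | 102 | 102/214 = 48% |
| 1 Aug | 112 | 41 | 41/153 = 27% |
| 10 Sep | 112 | 1 | 1/113 = 1% |
| 11 Sep or later | 112 or fewer | 0 | 0% |

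If start dates and onsets are assumed uniform (not in the documents), 54% of year-only Period 2 AEs are moved when Period 2 is counted to Week 32, and 50% when it is counted to Week 36. The remaining 46% to 50% fall in the next calendar year.

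**Case 2: year only, later year.** Start 02NOV2020; crossover 22FEB2021; onset 10MAR2021, recorded as 2021. The years differ. If the branches are nested as in the parallel concomitant-medication table, no rule applies.

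**Case 3: day missing, month of first infusion.** Onset that month cannot be in Period 2, because Period 1 lasts 112 days. There is no product error.

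**Case 4: day missing, crossover month.** Start 01FEB2021; crossover 24MAY2021; onset 28MAY2021, recorded as MAY2021. The month differs from that of treatment start, so on the nested reading the table is silent. If the general sentence fills the gap, the earliest date is 01MAY2021, which is Period 1 and wrong. Under the same uniform assumption, 10.5% (to Week 36) to 13.1% (to Week 32) of day-missing Period 2 AEs would move. If the closing branch is instead read as copying the day number of treatment start, the figures are 1.2% to 1.5%, and about 6% of day-missing Period 1 AEs would move to Period 2. The result depends on the reading, which shows that the case is unspecified.

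**Effect of one event.** If it is the subject's only event of its kind, the subject percentage changes by 1/20 = 5 points with 20 subjects, or 1/26 = 3.8 points with 26.

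**The case against.** The strongest reply is that this will almost never happen. AEs are assessed at visits normally one to two weeks apart, IgPro20 diaries record start and stop dates (Protocol 8.1.1.10), and doubtful entries are queried (Protocol 13.5.2). An onset whose month is unknown should be very rare. That stands, and it limits the point to a minor one.

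There are also safeguards. Listings show dates as recorded, a flag marks the level of imputation, imputed dates do not enter durations or elapsed times unless stated otherwise, and the Total column is unaffected by period. These let a reader trace an affected AE, but they do not correct the product columns.

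Two stronger readings are tempting, and neither is supported:

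- **That all partial dates are sent to first infusion and misallocated.** Day-missing dates are sent there explicitly only in the month of first infusion, where the product is right. The crossover-month error is an inference from the general sentence. The SAP does not say that this sentence fills gaps in the table.
- **That the rule biases a product comparison.** SAP 7.3 plans no hypothesis tests, and the primary objective is descriptive. Errors in the two sequences run in opposite directions and may partly offset in the pooled product columns. They do not offset in the by-period columns, where the year-only error always moves an event from Period 2 to Period 1.

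It is also fair to say that, with no washout, attribution by onset date close to Week 17 is itself a convention. That does not help an event months into Period 2 that is dated to the first infusion of the study.

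**Conclusion.** Wrong as written, minor. For a year-only start date in the calendar year of first dosing, the stated rules put the AE in Period 1 unless it ended before treatment. Any such Period 2 event is therefore counted under the wrong product, and no other section of the SAP corrects this. The Sequence B case matters most, because it removes an IgPro20 event from the primary safety tables.

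For months or years later than treatment start the finding is a gap, not a demonstrated error. Crossover-month dates default to Period 1 only if the general sentence is applied. Wholly missing start dates are a related gap: they can become TEAEs with no period or product.

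The number of affected AEs is not given and is probably very small. The percentages above rest on uniform start dates and onsets, and they describe the share of partial dates that would move, not how many there will be.

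**What to change.** Keep the present rule for the treatment-emergent flag only. For period and product allocation, add to SAP 8.1.2 and cross-refer from 8.3.1:

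1. Assign the AE to the only period compatible with the recorded date parts and the AE end date. An end date before crossover leaves only Period 1; a recorded month after the crossover month leaves only Period 2.
2. If both periods fit, use the visit at which the AE was first reported. Treat AEs recorded at Week 17 before the first Period 2 infusion as Period 1, since that visit collects AEs before dosing (Protocol 8.6.4.1 and 8.6.6.1).
3. If still unresolved, list the AE and show the IgPro20 and IgPro10 counts with it included under each product. Assigning all such events to IgPro20 would only replace one arbitrary allocation with another.

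The same steps cover later months and years and, for AEs deemed treatment-emergent, wholly missing start dates. The cost is a short SAP edit and one programming branch. Step 2 assumes that the visit of first report can be recovered from the eCRF or source records, which should be confirmed before programming.
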